Appendix I. RACD Individual questionnaire

1. Barcode: _____

This field should auto populate after Surveillance Agent clicks on 'Edit' button from RACD Household Level dashboard as barcode was already assigned.

2. Household ID: _____

This field should auto populate after Surveillance Agent clicks on 'Edit' button from RACD Household Level dashboard as Household ID was already assigned.

3. Consent obtained: Yes No Not yet

If no, trigger the Refuser Survey

Questionnaire will only be administered if household member is found at home. Auto-populate 'Not yet' option for consent obtained based on information collected from household level questionnaire. The 'Not yet' option must be greyed out (disabled) though showing that it was a previous selection option. Surveillance Agents must then either select 'Yes' or 'No', with the 'No' option triggering the refuser survey

4. Relation to index case (check all that apply):

Immediate Family Extended family Neighbor Visitor Co-worker Unknown

5. Nationality:

Swaziland Mozambique South Africa Other (specify _____)

(Provide drop down list of all nationalities)

6. Occupation (*Drop down list*):

Student Child or minor but not a student Unemployed
 Farming/Agriculture Manufacturing/Factory Other Manual Labor
 Small-market sales or trade Office or Clerical Work Other (specify _____)

7. Ask: Have you been diagnosed with malaria in the past 12 months? Yes No

If yes, ask when,

6 months to a year ago < 6 months ago Within the last month Within the last 2 weeks
 Don't know

If yes ask, have you had fever in the last 2 weeks? Yes No Don't know

If yes ask, have you been diagnosed with malaria in the last 2 weeks? Yes No Don't know

If diagnosed in the last 2 weeks:

Was the diagnosis confirmed by a test? Yes No Don't know

What treatment was prescribed? *Check all that apply*

Artemether-lumefantrine
 Single dose primaquine
 Oral Quinine
 IV Quinine
 IM Quinine
 IV Artesunate
 IM Artesunate
 Chloroquine
 SP/Fansidar
 Other (specify _____)
 Unknown

Was full treatment course completed? Yes No Don't know

Prior Residence and/or Travel History

8. Have you ever lived or stayed in Mozambique for at least 30 consecutive days?
If yes, approximately how long ago was this visit or stay? ___ yrs ___ mos

9. Have you spent at least one night anywhere else besides your current residence in the past 8 weeks?
 Yes No Don't know

- ***If no, skip to question 10.***

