Appendix K. TPE Individual questionnaire

1. Barcode: _____

This field should auto populate after Surveillance Agent clicks on 'Edit' button from TPE Household Level dashboard as barcode was already assigned.

2. Household ID: _____

This field should auto populate after Surveillance Agent clicks on 'Edit' button from TPE Household Level dashboard as Household ID was already assigned.

3. Consent obtained: Yes No Not yet

If no, trigger the Refuser Survey

Questionnaire will only be administered if household member is found at home. Auto-populate 'Not yet' option for consent obtained based on information collected from household level questionnaire. The 'Not yet' option must be greyed out (disabled) though showing that it was a previous selection option. Surveillance Agents must then either select 'Yes' or 'No', with the 'No' option triggering the refuser survey

4. Relation to index case (check all that apply):

Immediate Family Extended family Neighbor Visitor Co-worker Unknown

5. Nationality:

Swaziland Mozambique South Africa Other (specify _____)

(Provide drop down list of all nationalities)

6. Occupation (*Drop down list*):

Student Child or minor but not a student Unemployed
 Farming/Agriculture Manufacturing/Factory Other Manual Labor
 Small-market sales or trade Office or Clerical Work Other (specify _____)

7. Ask: Have you been diagnosed with malaria in the past 12 months? Yes No

If yes, ask when,

6 months to a year ago < 6 months ago Within the last month Within the last 2 weeks
 Don't know

If yes ask, have you had fever in the last 2 weeks? Yes No Don't know

If yes ask, have you been diagnosed with malaria in the last 2 weeks? Yes No Don't know

If diagnosed in the last 2 weeks:

Was the diagnosis confirmed by a test? Yes No Don't know

What treatment was prescribed? *Check all that apply*

Artemether-lumefantrine
 Single dose primaquine
 Oral Quinine
 IV Quinine
 IM Quinine
 IV Artesunate
 IM Artesunate
 Chloroquine
 SP/Fansidar
 Other (specify _____)
 Unknown

Was full treatment course completed? Yes No Don't know

Prior Residence and/or Travel History

12. Have you ever lived or stayed in Mozambique for at least 30 consecutive days?

If yes, approximately how long ago was this visit or stay? ___ yrs ___ mos

13. Have you spent at least one night anywhere else besides your current residence in the past 8 weeks?

Yes No Don't know

- ***If no, skip to question 10.***

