- *If yes, ask: Where did you sleep overnight, when did you sleep there, why did you sleep there, and personal protection? If slept outside Swaziland, also ask about means of travel and border post of re-entry.*

Within Swaziland				
Town / Locality / Inkhundla	Duration of Stay		Reason for sleeping away from current residence: -previous residence -business -holiday -visiting friends/family -other (specify, _____)	Personal protection -chemoprophylaxis (specify___) -bednet -mosquito repellent or coil -None
	First Night YY/MM/DD	Last Night YY/MM/DD		
a.				
b.				
c.				
d.				
e.				

Outside of Swaziland							
Country	Province / Town	Duration of Stay		Reason for sleeping away from current residence: -previous residence -business -holiday -visiting friends/family - Other (specify_____)	Personal protection (specify___) -chemoprophylaxis -bednet -mosquito repellent or coil -None	Means of travel -Large bus -Kombi (van) -Personal car -Ride share (catch a ride/got a lift) -Airplane -Bicycle -Walked -Other (specify_____)	Border Post of Re-Entry - Lavumisa/Golela - Salitje/Onverwacht - Mahamba - Gege/Bothashoop - Sicunusa/Houtkop - Sandlane/Nerston - Ngwenya/Oshoek - Bulembu/Josefsdal - Matsamo/Jeppe's Reef - Mananga - Lomahasha/Namaacha - Mhlumeni/Goba - KMIII International Airport - Other
		First Night YY/MM/DD	Last Night YY/MM/DD				
a.							
b.							
c.							
d.							
e.							

Medical History

10. *Weight:* ___ . ___ kg

Tablet should make this question compulsory for all ages

Ask the following questions to assess for potential criteria excluding participant from receiving antimalarial medication:

11. Are you pregnant or breastfeeding? Yes No Don't know

12. Have you menstruated in the past but not within the past 4 weeks? Yes No Don't know

13. Are you less than 9 months of age? Yes No Don't know

Tablet should automatically complete this question based on date of birth, select an option and not allow Agent to make changes

14. Are you allergic to have had a past adverse reaction to DP? Yes No Don't know

15. Have you already taken 2 courses of DP in the past year? Yes No Don't know

16. Have you taken DP within the last 2 months? Yes No Don't know

17. Do you have heart, kidney, or liver problems? Yes No Don't know

18. Does your family have a history of heart problems or sudden death? Yes No Don't know

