19. In the past month have you taken antimalarial drugs for either treatment or prevention of malaria (mefloquine, halofantrine, lumefantrine, chloroquine, or quinine)? Yes No Don't know

20. Have you had a fever in the past 48 hours, or are otherwise feeling ill? Yes No Don't know

If Yes, was subject taken to local health facility? Yes No

21. Are you currently taking any medications? Yes No Don't know

If Yes, are you taking any of the following medications? (check all that apply)

a. Medicines that effect heart rhythms (such as amiodarone, disopyramide, dofetilide, ibutilide, procainamide, quinidine, hydroquinidine, or sotalol)

b. Medicines that treat depression

c. Medicines that treat mental health problems (such as phenothiazines, sertindole, sultopride, chlorpromazine, haloperidol, mesoridazine, pimozone, or thioridazine)

d. Medicines that treat infection (macrolides [such as erythromycin or clarithromycin], fluoroquinolones [such as moxifloxacin or sparfloxacin], medicines for fungal infections [such as imidazole and fluconazole], as well as pentamidine [used to treat a specific type of pneumonia] and saquinavir [for treatment of HIV])

e. Antihistamines used to treat allergies or inflammation (such as terfenadine, astemizole, mizolastine)

f. Medicines that treat stomach problems such as cisapride, droperidol, domperidone, or diphemanil

g. Medicines to treat cancers (vinca alkaloids, arsenic trioxide), chest pain (bepridil), drug addiction (levomethadyl, methadone), and high cholesterol levels (probucole)

Drug Administration: (Subject is eligible to receive medication if they weigh at least 7kg and answered "No" to questions 10-19 and are not taking any of the medications listed in 20a-20g)

22. Is the subject eligible to receive medication? Yes No

Tablet to automatically say Yes or No for eligibility of individual to receive medication based on responses above and criteria provided, options should be greyed out (disabled).

a. *If yes, indicate regimen administered:*

Check one	Weight band	Color of box	Regimen administered	Subscription
	7-12 kg	Bottle	320 mg piperazine /40 mg dihydroartemisinin tablets, 3 half tablets	½ tablet daily x 3 days
	7-12 kg	Pink box	160 mg piperazine /20 mg dihydroartemisinin tablets, 3 tablets	1 tablet daily x 3 days
	13-23 kg	Green box	320 mg piperazine /40 mg dihydroartemisinin tablets, 3 tablets	1 tablet daily x 3 days

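### Appendix K's automatic DP-eligibility rule is numbered one too low, so fever or illness (question 20) falls outside the tablet's check

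*Combined protocol and SAP*

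**What the plan says.** The Drug Administration part of Appendix K sets two conditions besides a minimum weight of 7 kg: 'No' to "questions 10-19 and are not taking any of the medications listed in 20a-20g". Question 22 then has the tablet fill in the eligibility answer from the responses and the stated criteria, with the options disabled.

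The relevant parts of the same form are:

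- Question 10 is body weight in kg, with the instruction "Tablet should make this question compulsory for all ages".
- Next comes the heading of the exclusion block: "Ask the following questions to assess for potential criteria excluding participant from receiving antimalarial medication". Its first item is question 11 (pregnancy or breastfeeding) and its last yes/no item is question 20 (fever in the past 48 hours or otherwise feeling ill).
- Question 21 asks about current medicines and carries the lettered list a to g.
- Earlier in the form, two travel questions are printed with numbers that the exclusion block uses again: "12. Have you ever lived or stayed in Mozambique for at least 30 consecutive days" and "13. Have you spent at least one night anywhere else besides your current residence in the past 8 weeks". One of the exclusion items sharing those numbers is "12. Have you menstruated in the past but not within the past 4 weeks".

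Table 3 in section 4.5 lists a temperature of 38.0°C or more, reported fever in the past 48 hours, or other illness among the exclusions from DP.

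**The concern.** The text in Appendix K is a programming specification for a drug-eligibility decision, and its cross-references do not match the form. Question 20 lies outside the cited range, and the cited list 20a-20g does not exist. A programmer has to interpret the rule. The natural repair is to ignore the weight item and attach the medicine reference to the only list available, and that still leaves question 20 unchecked.

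Question 20 is not duplicated elsewhere on the form. Appendix K has no temperature field, and its only other fever question is nested under a reported malaria diagnosis in question 7. If the tablet does not use question 20, it can record a febrile or ill person as eligible for a drug that Table 3 withholds from them. Under section 7.3, people who cannot safely take DP are given a rapid test instead, so a wrong 'Yes' could also bypass that test.

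**Working it through.** No sample size, power or alpha figure is involved. The check compares the rule's numbers with the form's numbers.

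| Element | Rule cites | Form prints |
|---|---|---|
| Weight | at least 7 kg, as its own condition | question 10 |
| Yes/no exclusion items | 10-19 | 11-20 |
| Medicine list | 20a-20g | 21a-21g |

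**Is the rule wrong, or the form's numbering?**

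1. The range 10-19 spans 19 − 10 + 1 = 10 numbers. The exclusion block 11-20 holds 20 − 11 + 1 = 10 items. The cited list a-g has 7 entries, and so has the list under question 21. One uniform shift of one explains both mismatches.
2. Weight is already a condition in the rule and cannot be answered 'No', so question 10 cannot be meant as part of the range.
3. The pill-count table (question 25) takes the regimen from 22a, which is where the regimen table is printed.
4. The travel section says "If no, skip to question 10", which leads to the weight item. This is weaker support, because Appendix I carries the same instruction.

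The form's numbering of the medical block is therefore consistent, and the rule is out of step with it.

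**What the rule covers**

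- Exclusion items on the form: 10 (questions 11-20) + 7 (21a-21g) = 17.
- Rule as printed, with weight set aside and the medicine list recognised: 9 (questions 11-19) + 7 = 16. The missing item is question 20.
- Both references shifted by one: 10 + 7 = 17.

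**Is the corrected range unique?**

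- As the form is numbered now, 11-20 matches 10 exclusion items + 2 travel questions = 12 printed questions.
- Appendix I numbers the same travel questions 8 and 9; the first reads "8. Have you ever lived or stayed in Mozambique for at least 30 consecutive days". In Appendix K the item before them is question 7 and the item after them is question 10, so 8 and 9 are the vacant numbers.
- After renumbering, 11-20 matches exactly 10 questions.

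**The case against.** The strongest reply is that this is a clerical slip whose meaning is plain, in a form that staff use alongside a correct protocol. Much of that stands.

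- Table 3 states the fever and illness exclusion clearly. Section 7.3 withholds DP from anyone who cannot safely take it, although its own list of contraindications does not name fever or other illness. Section 7.4 refers febrile or ill people to a health facility. Section 8.1 has contraindications asked about before dosing. Question 20 itself prompts staff to record whether the person was taken to a facility.
- The timeline includes finalising the questionnaires, and section 13.1 provides for written procedures and training in tablet use. The slip may have been caught, though nothing in the documents shows that it was.
- The travel numbers look like list carry-over: Appendix I ends at 11 and these items resume at 12.

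A reader might infer more than the documents support, in three ways. First, that nobody could qualify, since a weight cannot be answered 'No'; but weight is a separate condition, so that is not a plausible reading. Second, that all seven medicine classes would also go unchecked; but the form has only one lettered medicine list, and it is printed directly above the rule. Third, that travellers would be refused DP because of the duplicated numbers; but the travel items stand under their own heading, before the exclusion block, and travel is not an exclusion in Table 3.

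The reply does not remove the remaining point. The safeguards act on staff conduct. None of them corrects a rule that sets the recorded answer in a disabled field.

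**Conclusion.** The rule is wrong as written, with limited practical risk. Both cross-references are one too low, and the realistic effect is that 1 of 17 exclusion items, question 20, is left out of the tablet's locked eligibility answer. This assumes that the programmer sets the weight item aside and recognises the medicine list under question 21. If the programmer instead shifted both references, nothing would be lost.

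The protocol's eligibility criteria are correct; the fault lies in the form's programming specification. The documents do not show how the tablet was coded, and the number of people affected cannot be derived from them. The primary outcome, power and alpha are untouched. The correction is worth making because the rule governs dosing with a drug that carries QT precautions and the change costs almost nothing.

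**What to change.** 1. Reword the eligibility rule in Appendix K to: weighs at least 7 kg, answered No to questions 11-20, and is not taking any medication in 21a-21g.
2. Renumber the two travel questions now printed as 12 and 13 to 8 and 9, as in Appendix I, so that the range 11-20 identifies only exclusion items.
3. Before use, check the tablet logic with one test case per exclusion item and one for a weight below 7 kg: 17 + 1 = 18 cases.

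The cost is one correction to the form and the tablet logic, plus a short test. It needs no extra visits, staff or participants.

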14.2 Outcome measures

Table 6. Outcome measures

Outcome	Indicator
Primary Aim	
Incidence	Cumulative incidence of all cases (Pf infection) identified by passive surveillance in the locality subsequent to the first reported case during the study period (not including additional cases found through RACD). Cases include both locally acquired and imported infections.
Secondary aims (effectiveness)	
Exposure (seroprevalence)	Seroprevalence to markers of recent exposure using ELISA in end-line survey samples taken from residents in Target Areas near the end of the study (expected mid 2017), excluding index cases detected through passive surveillance.
Infection prevalence	Prevalence of infection by LAMP and QTNASBA testing for gametocytes in LAMP positives in end-line survey samples taken from residents in Target Areas near the end of the study (expected mid 2017), including index cases detected through passive surveillance.
Time to first local post-intervention incident case	Time to first incident local case in the Target Area subsequent to the intervention. Target Areas that receive a repeat intervention will qualify to be included again at subsequent interventions.
Proportion of imported incident cases	Proportion of imported incident cases in the locality subsequent to the first reported case will be measured through passive surveillance. Additional cases found through RACD will not be included.
Transmission potential (by genotyping)	Microsatellite genotyping will be performed on samples collected from index cases as well as secondary cases.
Secondary aims (feasibility)	
Coverage	Proportion of persons residing within approximately 200m (TPE localities) or 500m (RACD localities) of the index case who consented to participate in the study and who completed the initial procedures for their study arm (finger prick for RDT in the RACD arm, initial dose of DP in the TPE arm)
Adherence	Proportion of persons who completed 3 days of therapy among all individuals initiated on DP in the TPE arm, as assessed by pill count
Prevalence of SAEs related to treatment	Proportion of subjects experiencing SAEs deemed possibly, probably, or definitely related to DP or AL, out of the total number of subjects enrolled
Acceptability	Qualitative assessment (See Section 10)
Cost	Cost per index case-level intervention, cost per case averted.

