	24-35 kg	Orange box	320 mg piperazine /40 mg dihydroartemisinin tablets, 6 tablets	2 tablet daily x 3 days
	36-74 kg	Purple box	320 mg piperazine /40 mg dihydroartemisinin tablets, 9 tablets	3 tablet daily x 3 days

	> 74 kg	Blue bag	320 mg piperazine /40 mg dihydroartemisinin tablets, 12 tablets	4 tablet daily x 3 days
--------------------------	---------	----------	---	-------------------------

NOTE: Give lower weight band if weight falls between weight bands.

NOTE: Use of the 320/40 mg or 160/20 mg tablet for children 7-12 kg will depend on drug availability.

b. Was dose #1 directly observed? Yes No, indicate reason _____

23. Comments or any other information that is relevant?

24. Modified DOT record

Encounter #	Date YY/MM/DD	Time ##:## AM/PM	Oversight (check one)	Comments
1			 Dose #2 DOT by study staff  Dose #2 Self-reported self-administration  Dose #2 Self-administered (reported by someone other than the subject)  Dose #2 Reminded patient to take drug  Dose #2 Indirectly reminded patient to take drug (via close contact)  Dose #2 Other, specify _____	
2			 Dose #2 DOT by study staff  Dose #2 Self-reported self-administration  Dose #2 Self-administered (reported by someone other than the subject)  Dose #2 Reminded patient to take drug  Dose #2 Indirectly reminded patient to take drug (via close contact)  Dose #2 Other, specify _____ <hr/>  Dose #3 DOT by study staff  Dose #3 Self-reported self-administration  Dose #3 Self-administered (reported by someone other than the subject)  Dose #3 Reminded patient to take drug  Dose #3 Indirectly reminded patient to take drug (via close contact)  Dose #3 Other, specify _____	

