3			 Dose #2 DOT by study staff  Dose #2 Self-reported self-administration  Dose #2 Self-administered (reported by someone other than the subject)  Dose #2 Reminded patient to take drug  Dose #2 Indirectly reminded patient to take drug (via close contact)  Dose #2 Other, specify _____ <hr/>  Dose #3 DOT by study staff  Dose #3 Self-reported self-administration  Dose #3 Self-administered (reported by someone other than the subject)  Dose #3 Reminded patient to take drug  Dose #3 Indirectly reminded patient to take drug (via close contact)  Dose #3 Other, specify _____	
Rx #3etc.			 Dose #2 DOT by study staff  Dose #2 Self-reported self-administration  Dose #2 Self-administered (reported by someone other than the subject)  Dose #2 Reminded patient to take drug  Dose #2 Indirectly reminded patient to take drug (via close contact)  Dose #2 Other, specify _____ <hr/>  Dose #3 DOT by study staff  Dose #3 Self-reported self-administration  Dose #3 Self-administered (reported by someone other than the subject)  Dose #3 Reminded patient to take drug  Dose #3 Indirectly reminded patient to take drug (via close contact)  Dose #3 Other, specify _____ Check one:  DOT by study staff  Self-reported self-administration  Self-administered (reported by someone other than the subject)  Reminded patient to take drug  Indirectly reminded patient to take drug (via close contact)  Other, specify _____	

For return visits for DOT, allow editing of above table for all individuals.

25. Pill count

Date of pill count	Regimen administered	Is your medication packaging still available?	IF blister pack available, count number of pills remaining	IF blister pack not available, Ask: Approximately how many pills did you take?	Other comments

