DD/MM/YY	automatically generated per 22a	 yes  no	half tabs  1  2  3 full tabs (120/20 or 320/40)  0  1  2  3  4  5  6  7  8  9	half tabs  1  2  3 full tabs (120/20 or 320/40)  0  1  2  3  4  5  6  7  8  9	

For return visits for pill count, allow editing of above table for all individuals.

26. Ask: Have you experienced any potential side effects from the medication?

Yes No

26a If YES, specify:

- cough
- fever
- headache
- lack of energy
- abdominal pain
- pale complexion or pallor
- yellow discoloration of skin or eyes (jaundice)
- weakness
- joint pain
- dark urine
- nausea
- vomiting
- diarrhea
- chest pain
- heart palpitations
- other (specify _____)

If YES, complete Appendix S. **Adverse drug reaction (ADR) Report Form**

27. Please explain all measures taken to alleviate these adverse reactions related to the drug

28. Other comments _____

Thank you for our participation in this study.

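### The pill-count form has no box for 0 half tablets remaining or for 10 to 12 tablets taken, so some fully adherent participants may be lost or miscoded

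*Combined protocol and SAP*

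**What the plan says.** Table 6 in section 14.2 defines adherence as the proportion completing three days of therapy among those started on DP, "as assessed by pill count". Sections 3 and 7.5 hypothesise 80%. Section 14.3 plans 5-point absolute precision with 532 people.

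Question 22a of Appendix K lists six regimens. The smallest is "320 mg piperazine /40 mg dihydroartemisinin tablets, 3 half tablets", with a bottle as packaging. The largest, for participants above 74 kg, is "320 mg piperazine /40 mg dihydroartemisinin tablets, 12 tablets" ("4 tablet daily x 3 days"), with a bag as packaging.

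Question 25 shows the regimen ("automatically generated per 22a") and asks whether the medication packaging is still available. It then has two alternative columns. One is headed "IF blister pack available, count number of pills remaining", the other "IF blister pack not available, Ask: Approximately how many pills did you take". Both print the same boxes: 1, 2, 3 for half tablets, and 0 to 9 for full tablets under "full tabs (120/20 or 320/40". A column for other comments follows. No section says how a blank or an out-of-range count is scored.

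**The concern.** The boxes are identical in a column where success means 0 and in a column where success means the whole regimen. For two regimens, one of those success values is missing. The half-tablet list starts at 1, although the full-tablet list beside it starts at 0. The full-tablet list stops at 9, although one regimen has 12 tablets.

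The gap is not neutral. In the failing columns, the people who cannot be entered are those who completed treatment, plus those who took 10 or 11 of 12. Other non-completers can be entered. If the blank is scored as non-adherence, or if someone ticks 9 because it is the highest box, the estimate falls. If blanks are dropped, completers are removed selectively and the estimate still falls, though by less. At stake is one secondary feasibility outcome, to be set against an 80% hypothesis.

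A separate labelling conflict sits in the same boxes. The strength 120/20 appears nowhere else. Section 7.3, question 22a and Appendix Q name a 160/20 tablet. This does not change a count of tablets, but the passages must be reconciled.

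**Working it through.** **1. Regimen totals (question 22a).** Half tablets: 1 a day × 3 days = 3 halves. Above 74 kg: 4 a day × 3 days = 12 tablets. Both agree with the totals printed on the form.

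**2. Can full adherence be ticked?**

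| Regimen | Total | Remaining = 0 | Taken = total |
|---|---|---|---|
| 7–12 kg, half tablets | 3 halves | **no** (boxes 1–3) | yes |
| 7–12 kg, 160/20 tablets | 3 | yes | yes |
| 13–23 kg | 3 | yes | yes |
| 24–35 kg | 6 | yes | yes |
| 36–74 kg | 9 | yes | yes |
| > 74 kg | 12 | yes | **no** (boxes 0–9) |

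Ten of 12 cells work. Each affected regimen fails in one column only. In the taken column of the 12-tablet regimen, 10 and 11 are also missing.

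**3. Is the 0–9 range too short for tablets remaining?** Section 7.3 has the first dose directly observed. After 4 of 12 tablets, at most 12 − 4 = 8 remain, so 0–9 is enough in that column.

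**4. Possible bias.** The documents give neither a weight distribution nor a rate of packaging return, so the following are assumptions:

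- True adherence is 80%, the plan's own hypothesis.
- A share s of those counted is in the two regimens, with s = 5 to 15%. Of the 660 people expected in section 14.1 (22 × 30), that is 33 to 99.
- A fraction r of that share falls in the failing column.

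*Unrecordable completers scored non-adherent:* observed adherence = 0.80 × (1 − s × r), so the loss is 0.80 × s × r.

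- r = 0.5: 0.80 × 0.05 × 0.5 = 2 points; 0.80 × 0.15 × 0.5 = 6 points.
- r = 1: 0.80 × 0.05 = 4 points; 0.80 × 0.15 = 12 points.

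*Unrecordable completers dropped as missing:* observed adherence = (0.80 − 0.80sr) / (1 − 0.80sr).

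- r = 0.5: 0.78/0.98 = 79.6%, loss 0.4; 0.74/0.94 = 78.7%, loss 1.3.
- r = 1: 0.76/0.96 = 79.2%, loss 0.8; 0.68/0.88 = 77.3%, loss 2.7.

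*Counts recovered from the comments column:* loss 0.

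**5. Which r is plausible?** The two failures need opposite packaging states: half tablets fail when packaging is present, the 12-tablet regimen when it is absent. If the two groups are equal in size and packaging is present for a fraction q in each, then r = 0.5q + 0.5(1 − q) = 0.5 whatever q is. So r = 0.5 is a reasonable central value under those assumptions, and r = 1 is an upper bound.

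**The case against.** The strongest reply is that neither group is shut out. Three half tablets taken can be ticked, and so can 0 of 12 remaining. Half tablets come from a bottle. On a literal reading of the blister-pack condition, those children go to the taken column, which works. The form also says that the choice between half and smaller tablets at 7–12 kg depends on drug availability, so the half-tablet group may be small. The regimen is pre-filled, comments can be written, the table can be edited at return visits, and question 24 records doses 2 and 3. A blank could therefore be queried.

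Most of this stands, and it limits the point. It does not remove it. The opening question asks about packaging in general, while the column headings speak of a blister pack, so the routing of bottle users is ambiguous. No section requires the count to be written in comments, or says that question 24 may replace the pill count that Table 6 names.

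A reader might go further and infer that the form cannot record full adherence for these groups at all, that all of them will be scored non-adherent, or that an assumed share of 5 to 15% means a loss of 5 to 15 points. The documents do not support this. Each group has a working column, and no scoring rule turns a blank into a failure. A loss equal to the full share would need everyone in the two groups to be adherent, in the failing column and scored as a failure. At 80% adherence the ceiling is 4 to 12 points. Nor is a count above 9 remaining a practical gap once the first dose has been observed.

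**Conclusion.** The options in question 25 do not match the regimens in question 22a, and this is wrong as written. Some, not all, fully adherent participants on the half-tablet and 12-tablet regimens may be missing or miscoded, and the likely direction is towards lower adherence.

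The size cannot be fixed from the documents. Under the assumptions shown, it runs from zero, through 0.4 to 2.7 points if blanks are dropped, to 2 to 6 points if half of these participants meet the failing column and are scored non-adherent. The last range straddles the planned 5-point precision; the 4 to 12 points at r = 1 is an upper bound. The matter is minor: it touches one secondary feasibility outcome and leaves the primary incidence comparison unaffected.

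**What to change.** In both columns of question 25, offer 0–3 for half tablets and 0–12 for full tablets, so that the boxes cover every regimen printed in question 22a. Replace the blister-pack condition with wording that covers bottle and bag as well, consistent with the packaging question before it. Have the device check each entry against the pre-filled regimen total. Reconcile the 120/20 label with the 160/20 tablet named in section 7.3, question 22a and Appendix Q. Add one sentence to section 14.4 on how blank or out-of-range counts are scored.

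The cost is a form edit, a validation rule and one sentence, with no effect on design or sample size. If forms have already been used, counts for these two regimens should be checked against the comments column and the dose record in question 24. Any that cannot be recovered should be reported as such, with adherence shown under both scorings.
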